1.5 Rationale for Study

Granulocyte macrophage-colony stimulating factor is considered to play a major role in disease pathogenesis in RA. CAM-3001 blocks cellular activation by GM-CSF through its binding to the GM-CSF receptor, and hence, may provide clinical benefit to patients with moderate-to-severely active RA who need disease control. Further clinical development of CAM-3001 is supported by the safety profile observed in a Phase 1 study (CAM-3001-0702).

MI-CP219 will be the first study to test the efficacy and safety of SC administered CAM-3001. The study is intended to provide efficacy and safety data over a range of doses to enable progression of the clinical development program. The effects of CAM-3001 on validated RA clinical outcomes, dose identification and the PK, PD and immunogenicity of CAM-3001 in this subject population will be assessed. In addition the study includes scheduled data reviews of available safety data across the range of doses, and exploratory analyses of relationships between CAM-3001 exposure, GM-CSFα receptor occupancy, inhibition of GM-CSF gene signature and micro RNA (miRNA) expression, which will assist in dose selection for future studies.

MedImmune CAM-3001

MedImmune CAM-3001 **1.5.1 Dose Justification**

In this Phase 2 study, CAM-3001 will be administered SC at fixed doses of 10 mg, 30 mg, 50 mg or 100 mg every other week, based on the PK/PD simulations and nonclinical/clinical safety considerations.

From in vitro studies and literature, 10% of available GM-CSFR α is adequate to elicit maximum biological activity. Therefore, it is assumed that inhibition of macrophage activity with CAM-3001 would require at least 90% receptor blockade. Furthermore, preclinical investigations of CAM-3001 in non-human primates, has shown a dose and time dependant effect on alveolar macrophages, which in absence of GM-CSF stimulation, become unable to process surfactant and assume the characteristic "foamy" appearance due to its accumulation in these cells. This is predictable based on the pharmacology of inhibiting normal GM-CSF function (Yoshida et al., 2001). In these preclinical investigations, there were no changes in clinical observations, body weights, clinical pathology parameters, urinalysis, immunophenotyping, organ weights, macroscopic observations, or microscopic findings in any other tissues.

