A population PK model was constructed using data from the FTIH study in subjects with RA (CAM-3001-0702) to describe the PK of a typical human IgG4, binding of CAM-3001 to GM-CSFR α , and the internalisation of GM-CSFR α and CAM-3001/ GM-CSFR α complex. The population PK model was then used to predict the PK profiles of CAM-3001 for this study, assuming a 65% SC bioavailability (typical for IgG) and 80 kg average body weight.

Based on this model, the predicted GM-CSFR α receptor occupancy profiles upon multiple SC administrations of CAM-3001 show that doses above 30 mg SC every other week achieve \geq 90% receptor occupancy systemically. An initial dose of 10 mg is predicted to induce transient and < 90% GM-CSFR α occupancy in RA patients and offers a cautious approach to subject safety. Doses of 10, 30, 50 and 100 mg of CAM-3001 SC every other week provide an adequate dose range to demonstrate a PD effect systemically (including synovial tissue) but limit lung concentrations because of limited partitioning of CAM-3001 to the alveolar space. The lung:serum partitioning for other IgG monoclonal antibodies developed by MedImmune have been approximately 1:50 for lung tissue, 1:200 for sputum, and 1:1000 for bronchoalveolar lavage (BAL) fluid. Partitioning to synovial fluid is expected to be approximately 1:4.

MedImmune Protocol MI-CP219: Amendment 3 CAM-3001 The safety margin was calculated based on the comparison of observed TK exposure in a multiple-dose GLP study in cynomolgus monkeys at the NOAEL (15 mg/kg/week) and model predicted steady-state PK exposure in subjects with RA upon biweekly SC

administrations of CAM-3001. The estimated safety margins for MI-CP219 are listed in Table 1.5.1-1.

Final

					-		•	0	
	Predicted steady-state human exposure (EOW SC)			15 mg/kg NOAEL in Cynomolgus monkeys	Safety	⁷ Margir	n for MI	-CP219	
	10mg	30mg	50mg	100mg		10mg	30mg	50mg	100mg
AUCτ (μg d/mL)	2.39	20.8	58.9	162	12900*	5400	620	219	79.6
Cmax (µg/mL)	0.514	2.55	5.97	15.1	1260	2450	494	211	83.4

Fable 1.5.1-1 Predicted Human Exposure and Calculated Safe	ty Marg	gin
--	---------	-----

 AUC_{τ} = area under the concentration-time curve at steady-state in the 14-d dosing interval; C_{max} = maximal observed concentration EOW - every other week; NOAEL = no observed adverse effect level; SC = subcutaneous.

* Steady-state AUC in a 2-week interval

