3.1 Overview of Study Design

This is a multicentre, randomised, double-blind, placebo-controlled study to evaluate the efficacy and safety of multiple ascending SC doses of CAM-3001 in combination with stable methotrexate in subjects aged 18 to 80 years of age with active RA.

Protocol MI-CP219; Amendment 3 Final

Approximately 72 sites worldwide may be involved in the study. A total of 216 subjects will be recruited into 4 cohorts of 54 subjects to receive either 10 mg, 30 mg, 50 mg or 100 mg SC doses of CAM-3001 or placebo every other week for 12 weeks. All cohorts will be randomised in a 2:1 ratio (active:placebo). For Cohorts 1 to 3, decisions relating to dose escalation will be made by the sponsor (including the medical monitor, the safety physician, the project medical director and additionally final approval by the MedImmune Safety Monitoring Committee (SMC) which includes internal and external experts). These reviews of all cumulative safety data will occur after at least 18 subjects have completed dosing on Day 29. In Cohort 4, an initial 18 subjects will be recruited; once at least 6 of these subjects have been exposed to investigational product for the entire treatment period (Day 85) and no safety concerns have been detected, randomisation will resume to enrol the remaining number of subjects planned for this cohort.

Additional subjects will be recruited at sites in Japan. A total of 48 subjects from Japan will be randomised into 4 cohorts in a 2:1 ratio (active:placebo) with a total of 12 subjects per cohort. Details are included in a local protocol amendment for Japan.

The assigned dose of CAM-3001 or placebo (1 mL) will be administered as SC injections in the upper arm, thigh, or abdomen. The intention of the protocol is that subjects will be maintained on the same stable dose of concomitant RA treatment from Screening until Day 85. Adverse events and SAEs will be collected from the time of consent until the end of the safety follow-up period. Disease activity will be assessed throughout the treatment period and during safety follow-up. The schedules of subject evaluations are presented in Table 5.2-1.

Cumulative safety data will be reviewed by the sponsor continuously throughout the study. Formal safety reviews will include all subjects in the study at the data cut-off irrespective of the number of doses that subjects have received at that point.

Cohort 1

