7.3.1 Primary Endpoint

7.3.1.1 Efficacy

The primary efficacy objective will assess DAS28 response rates of CAM-3001 treated subjects compared with subjects who received placebo on the day of last dose of investigational product (Day 85). According to the EULAR response criteria an improvement from baseline in DAS28 of more than 1.2 would be considered a good response in subjects experiencing low disease activity (baseline DAS28 < 3.2) and a moderate response in subjects experiencing medium-to-high disease activity (baseline DAS28 \geq 3.2). A responder will be defined as a subject experiencing a decrease of more than 1.2 from their baseline DAS28 score, on the day of last dose of investigational product (Day 85).

Evaluable subjects will be cross-classified in a two-by-two contingency table according to their combined treatment group (CAM-3001 or Placebo) and by their responder status (Yes or No). The DAS28 response rate at Day 85 between combined CAM-3001 and combined placebo treatment groups will be compared using a two-sided Fisher's exact test.

Following the above comparison between the combined CAM-3001 and combined placebo treatment groups, each applicable dose cohort and the combined placebo group will be compared. These comparisons at the dose cohort level are not powered and as such their results will be considered in an exploratory setting. There will also be no adjustment for multiplicity. A 95% confidence interval of difference in DAS28 response rate between CAM-3001 and placebo treatment groups will be computed for each dose cohort to estimate the effect size of each CAM-3001 dose level.

The DAS28 response rate at Day 29 between CAM-3001 and placebo will also be compared using a Fisher's exact test.

To check the sensitivity of the comparisons, all the above analyses will be repeated over the respective cohort groupings but in the more restrictive ATP population. Due to the definition of the ATP population no imputation of the DAS28 score is needed for these analyses.

MedImmune CAM-3001 **7.3.1.2 Safety**

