7.4 Sample Size

The primary objective of the study is to evaluate safety, tolerability and efficacy of multiple doses of CAM-3001. No formal sample size calculation was performed for the primary objective of safety.

With respect to the primary efficacy analysis (Day 85), 216 subjects will be randomised to achieve at least 180 evaluable subjects, allowing for a 15% rate of drop outs. A further 48 subjects will be randomised in Japan to give an overall sample size of 264 subjects in 4 equal sized cohorts of 66 subjects.

The sample size computation for the primary efficacy endpoint of the study is based on the objective of evaluating the effect of CAM-3001 on the response rate in terms of improvement in DAS28 score at Day 85. A responder will be defined as a subject experiencing a decrease from baseline in DAS28 score at Day 85 of more than 1.2. Assuming a placebo response rate of 10%, a combined CAM-3001 response rate of 30%, a two sided Type 1 error of 0.05, 86% power, and a 2:1 (active: placebo) randomisation ratio, a total sample size of 180 subjects (120 active: 60 placebo) will be required to detect a 20% difference in response rates for an analysis based on two-sided Fisher's exact test.

The sample size of 216 evaluable subjects (144 CAM-3001 subjects and 72 placebo subjects) including Japanese subjects will have 92% power with Type 1 error of 0.05, using a two-sided Fisher's exact test on the primary efficacy endpoint of comparing DAS28 response rates between the combined CAM-3001 and combined placebo groups.

MedImmune will be unblinded at the primary analysis (Day 85), excluding subjects enrolled in Japanese sites. The data from the primary analysis will not be communicated to personnel

MedImmune CAM-3001 at the Contract Research Organisation or investigational sites or to enrolled subjects. The purpose of this analysis is for internal decision making on the progression of the clinical programme, so this analysis will not impact the conduct of the current study. This is the final analysis of the primary efficacy endpoint, so no alpha adjustment for analysis will be made.

A further analysis may be performed when all randomised subjects, excluding randomised subjects in Japan, have completed all study assessments.

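### Each dose is estimated only against placebo pooled over sequential cohorts, so the dose-level estimates can absorb calendar-time drift; the combined test ignores cohort but is not biased by it

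*Protocol*

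**What the plan says.** Protocol section 3.1 fixes the allocation: "All cohorts will be randomised in a 2:1 ratio (active:placebo"). The flow diagram notes in section 3.1 and section 4.5.5 make the cohorts sequential. The next dose opens once at least 18 subjects have been dosed at Day 29, and Cohort 4 pauses after 18 subjects until at least 6 have been exposed to Day 85. Each dose is given in one cohort only, beside that cohort's own placebo subjects.

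Section 7.3.1.1 puts evaluable subjects into a single two-by-two table: "The DAS28 response rate at Day 85 between combined CAM-3001 and combined placebo treatment groups will be compared using a two-sided" Fisher's exact test. It continues: "each applicable dose cohort and the combined placebo group will be compared". The dose-level comparisons are declared exploratory, unpowered and unadjusted for multiplicity, yet a 95% confidence interval per dose is to serve as the estimate of that dose's effect size. The sensitivity analysis repeats the same contrasts in the ATP population. Section 7.3.2.1 uses the combined placebo group as comparator for the other disease-activity analyses. No comparison with a cohort's own placebo and no adjustment for cohort is described. Exploring the relation of dose to efficacy is secondary objective 2 (section 2.2).

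**The concern.** The randomised control for a given dose is the placebo group of its own cohort. With equal cohorts, that group is only a quarter of the pooled comparator (15 of 60 evaluable placebo subjects); the rest were randomised in other cohorts, at other times. If response rates shift over the recruitment period, for instance through a change in sites, case mix or assessor habits, the shift enters each dose estimate. Doses ascend with time, so a steady rise in response looks like a rising dose response and a steady fall hides one. A sponsor choosing a dose from these intervals would have no display that separates the two.

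A second, smaller matter is that cohort is a stratum of the randomisation and the combined test leaves it out.

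**Working it through.** **Inputs.** Section 7.4 takes response to be 10% on placebo and 30% on CAM-3001 over all doses, with α = 0.05 (two-sided), a power of 86% and twice as many active as placebo subjects. Its result is 180 evaluable subjects, split 120:60. Four equal cohorts give 180/4 = 45 evaluable each, taken as 30 active and 15 placebo. No drift figure is given, so the drift paths below are assumptions.

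**1. The plan's own power.** Exact power is Σx Σy Bin(x; 120, 0.30) · Bin(y; 60, 0.10) · 1{two-sided Fisher p ≤ 0.05}.
- 120:60 gives 87.8% (stated 86%).
- 144:72, with Japan, gives 93.6% (stated 92%).
- Both are met. The true size at 120:60 is 3.4% at a common rate of 10% and 4.1% at 30%, so Fisher's test is conservative.

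**2. Bias in the combined contrast.** Let r1 to r4 be the response rates in the four cohorts with no drug effect. Under 2:1 in every cohort, both arms carry the same cohort weights, so the expected difference is (r1+r2+r3+r4)/4 − (r1+r2+r3+r4)/4 = 0. Simulation (200,000 trials per scenario) confirmed zero bias, and Fisher size stayed at 3.2–3.4%.

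**3. Bias in dose k against pooled placebo.** With no drug effect, the expected difference is r_k − (r1+r2+r3+r4)/4. False-positive rates are exact, for a two-sided Fisher test at 30:60.

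| Assumed response, Cohorts 1–4 | Mean | Bias at 10, 30, 50, 100 mg (points) | False positives, 10 mg | False positives, 100 mg |
|---|---|---|---|---|
| 5, 8.3, 11.7, 15% | 10% | −5, −1.7, +1.7, +5 | 5.7% | 8.5% |
| 5, 10, 15, 20% | 12.5% | −7.5, −2.5, +2.5, +7.5 | 11.5% | 12.9% |

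Without drift, at a 10% rate, the same test rejects about 3.1% of the time. The false gradient from 10 mg to 100 mg is 5 − (−5) = 10 points in the first row and 7.5 − (−7.5) = 15 points in the second. Against own-cohort placebo the expected difference is r_k − r_k = 0 for every dose.

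**4. Cost of the own-cohort contrast, at 30% against 10%.**
- Fisher power is 61% at 30:60 and 25% at 30:15.
- Approximate 95% half-width, 1.96·√(0.3·0.7/30 + 0.1·0.9/n): 18.1 points for n = 60 and 22.3 points for n = 15.

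**5. Stratifying the combined test.** The CMH statistic is [Σ(a_k − E_k)]²/ΣV_k, with a_k the active responders and m_k all responders in cohort k, E_k = m_k·30/45 and V_k = m_k(45 − m_k)·30·15/(45²·44). Simulated power (200,000 trials) at 30% against 10%, no drift:
- CMH without continuity correction 89.5%
- unstratified Pearson chi-square 89.6%
- pooled Fisher 87.8%
- CMH with continuity correction 84.6%

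The gain over Fisher is 89.5 − 87.8 = 1.7 points. Pearson matches CMH, so the gain comes from dropping Fisher's conservatism and not from stratifying. With placebo drifting from 5% to 15% and a constant 20-point effect, CMH gives 89.8% and Fisher 87.9%.

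**The case against.** The other side has weight. The protocol itself calls the dose-level comparisons exploratory and unpowered. Drift is hypothetical. Pooling placebo is a familiar trade of some bias for precision, and step 4 shows what it buys. Since each dose exists in one cohort only, adjusting fully for cohort reduces to the own-cohort contrast, so no model keeps all the precision and removes all the bias. Fisher's test is exact and meets its stated power. An SAP that is not shown may add displays.

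Most of this stands, and it is why the pooled contrasts should stay. It does not settle the point. The exploratory label answers multiplicity and power, not bias, and the intervals are meant to estimate each dose's effect. The protocol fixes the pooled comparator itself; it does not leave that choice open.

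Three stronger readings are tempting and are not supported:
- A reader might infer that calendar time confounds the primary test. It does not, because 2:1 allocation holds in every cohort (step 2).
- A reader might infer that the 86% is wrong because 10 mg dilutes the effect. Section 1.5.1 says "it is assumed that inhibition of macrophage activity with CAM-3001 would require at least 90% receptor blockade" and "An initial dose of 10 mg is predicted to induce transient and < 90" per cent occupancy. But section 7.4 already states its 30% as a combined rate over the doses. A weak 10 mg arm is a different alternative hypothesis, not an error in the calculation.
- A reader might infer that a formal multiple-contrast dose-response test is required. The objective is only to explore dose, and such a test built on pooled placebo would carry the same drift.

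**Conclusion.** The point holds for the dose-level estimates. As planned, they mix dose with calendar time. Under the assumed drifts the bias at the extreme doses is 5 to 7.5 points in opposite directions, against a planned effect of 20 points, and the false-positive rate at 100 mg is 8.5–12.9%. With no drift there is no bias. The protocol does not say whether a cohort must be full before the next opens; overlap would reduce the drift between cohorts.

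The combined primary comparison is unbiased and adequately powered on the plan's own inputs. Leaving cohort out of it costs about 2 points of power at most under these assumptions, nearly all of it due to Fisher's conservatism. The results assume 30:15 evaluable in each cohort. If evaluability departed from 2:1 differently across cohorts, a small bias could enter the combined contrast, and stratification would guard against that.

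**What to change.** In section 7.3.1.1:

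(a) For each dose, report the risk difference and 95% confidence interval against its own cohort's concurrent placebo beside the pooled-placebo contrast, and state that the dose relation will be read from both. Agreement supports the pooled estimate; disagreement points to drift. Listing the placebo response rate by cohort would show drift directly.

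(b) Stratify the combined comparison by cohort, and by Japan as well in the final analysis, using a CMH test that is stated to be without continuity correction. With the correction it would have less power than the planned test (84.6% against 87.8%). Section 7.4 should then note that its power figures were derived for Fisher's test, which can be kept as a sensitivity analysis.

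The cost is wording and a little programming, settled before the sponsor is unblinded at the Day 85 analysis. The downside of (a) is precision: own-cohort half-widths of about 22 points against 18, and power per dose of about 25% against 61%. They therefore supplement the pooled contrasts and do not replace them. The downside of (b) is that a large-sample test replaces an exact one; its simulated size was 5.1% at a common rate of 10%.

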7.3.2 Secondary Endpoints

The secondary endpoints of this study include disease activity, the onset of response, duration of response after withdrawal of treatment, need for additional medications during the study and the PK and immunogenicity of multiple SC doses of CAM-3001.

The onset of response, duration of response after withdrawal of study treatment and need for additional medications during the study (Yes/No) will be summarised and tabulated together with descriptive statistics and listed by treatment arms. The time-to-events endpoints; the onset of response, duration of response after withdrawal of treatment will be analysed using non-parametric log-rank method and also Cox proportional hazard models (modelling baseline covariates as appropriate).

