7.3.2.1 Disease Activity

The major clinical measures of RA disease activity will be summarised descriptively by treatment group and time and include ACR20, ACR50, and ACR70 responses and DAS28 responses, including moderate and good responses, and complete clinical responses.

The ACR20, ACR50, and ACR70 binary responses will be compared between the CAM-3001 and placebo treatment groups using the Fisher's exact test at each study time point.

Protocol MI-CP219; Amendment 3 Final

The ACR response at Days 29, 43, 57, 71, 85, 99, 113, and 169 will also be analysed as a continuous variable. An appropriate continuity correction maybe applied if the data are interval bound or discrete. The ACR response will be compared between the CAM-3001 and placebo treatment groups using a repeated measures model.

The DAS28 responses at various study time points other than Day 29 and Day 85 will also be compared between the CAM-3001 and placebo treatment groups using the methodology described in the secondary endpoint analysis section, although no imputation will be used in these analyses.

The DAS28 responses will be compared between the CAM-3001 and placebo treatment groups according to the EULAR response criteria at certain study time points using a Cochran-Mantel-Haenszel test.

All the modelling and other comparative analysis described above will be conducted over the appropriate dose cohort groupings and time points as noted above. Each analysis will first compare between the combined CAM-3001 and combined placebo treatment groups. The analysis will then be conducted separately comparing combined placebo group and each of the applicable dose cohorts. Most of the above analysis will be conducted over both the evaluable and ATP populations. Details of all these analyses will be described in the SAP.

The predicted DAS28 and ACR values from the models above will be compared to the actual values observed at Day 85, and Day 169 for subjects in Cohort 3 as they become available. This will test the predictive capability of such models and will also help calibrate them as necessary.

Core components of the ACR and DAS28 responses will be summarised descriptively by treatment group and time and change from baseline. Levels of rheumatoid factor, anti-CCP antibodies, ESR, and subject's need for rescue corticosteroid therapy will be summarised descriptively by treatment group and time point and change from baseline.

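### Testing duration of response after withdrawal by log-rank and Cox would, on its natural reading, compare CAM-3001 and placebo responders selected after randomisation, so the result has no randomised interpretation

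*Protocol*

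**What the plan says.** Protocol section 7.3.2 names onset of response and duration of response after withdrawal as time-to-event endpoints. For the second it fixes the method: "duration of response after withdrawal of treatment will be analysed using non-parametric log-rank method and also Cox proportional hazard models". The Cox model comes with "modelling baseline covariates as appropriate", and no covariate is named. The same paragraph says that these endpoints "will be summarised and tabulated together with descriptive statistics and listed by treatment arms".

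Section 7.3.2.1 sets an order for its comparative analyses: "Each analysis will first compare between the combined CAM-3001 and combined placebo treatment groups". Each dose cohort is then set against combined placebo.

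Section 7.3.1.1 defines response: "A responder will be defined as a subject experiencing a decrease of more than 1.2 from their baseline DAS28 score", judged on the day of the last dose, Day 85. That section calls only the dose-cohort comparisons of DAS28 response rate unpowered and exploratory. Nothing comparable is said of duration. The protocol does not give subjects without a response a duration of zero.

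**The concern.** A subject who is not in response when dosing stops has no response to lose. The subjects at risk in a duration analysis are therefore the Day 85 responders, and being one is a result of treatment. With a working drug, the placebo responders are a small group who improved without it. The active responders are a larger group that includes people who would not have responded on placebo. The two groups are no longer comparable by randomisation.

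Log-rank and Cox methods would still give a p-value and a hazard ratio. Either could be read as showing that the drug's effect lasts, or fades, when it may reflect only who became a responder. Section 5.1.1.2 lists this endpoint among those used to explore dose and efficacy, so a misleading figure could carry weight.

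**Working it through.** **1. The plan's own figure.** Inputs from section 7.4: response 10% on placebo and 30% on CAM-3001, two-sided 5% level, Fisher's exact test, 120:60 evaluable, and 144:72 with Japan. Exact enumeration, doubling the one-sided p-value, gives power of 86.1% and 92.2%, against the stated 86% and 92%. The minimum-likelihood form of the test gives 87.8% and 93.6%. The stated figures reproduce, so the same rates are used below.

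**2. Expected responders = evaluable number × response rate.**

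| Analysis | CAM-3001 | Placebo |
|---|---|---|
| Final, 144:72 | 144 × 0.30 = 43.2 | 72 × 0.10 = 7.2 |
| Without Japan, 120:60 | 120 × 0.30 = 36 | 60 × 0.10 = 6 |

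The final analysis is the relevant one, because duration runs to Day 169. The central 95% binomial range for placebo responders is 3 to 13 of 72, or 2 to 11 of 60. The chance of three or fewer is 6% with 72 placebo subjects and 14% with 60. One dose cohort at the 120:60 size has 30 evaluable active subjects, so about 30 × 0.30 = 9 active responders against 6 placebo.

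**3. How selection can distort the contrast.** This is an illustration under an assumption, not an estimate. Let response depend equally on a standard normal prognosis and independent standard normal noise, and let the drug only move the response rate from 10% to 30%. With response probability p, mean prognosis among responders is φ(z) / (p√2), where z is the standard normal point exceeded with probability p.

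- Placebo: φ(1.282) / (0.10 × 1.414) = 0.1755 / 0.1414 = 1.24 SD.
- CAM-3001: φ(0.524) / (0.30 × 1.414) = 0.3477 / 0.4243 = 0.82 SD.

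The responder groups differ by 0.42 SD although the arms were identical at randomisation. If better prognosis lengthens persistence, a drug with no effect on persistence would appear to shorten it. A different model would give a different size.

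**4. Can covariates repair it?** Only as far as measured baseline variables explain response. With about 7 placebo responders, very few terms can be fitted.

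**5. Information available (context only).** Schoenfeld power is Φ(√(d·a(1−a))·|ln HR| − 1.96), with d events and active fraction a. As a best case, every responder is taken to lose response.

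- 144:72: d = 50.4, a = 43.2/50.4 = 0.857. √(50.4 × 0.857 × 0.143) × 0.693 = 1.72, so power at a hazard ratio of 0.5 is Φ(−0.24) = 41%.
- 120:60: d = 42, same a. √(42 × 0.857 × 0.143) × 0.693 = 1.57, so power is Φ(−0.39) = 35%.
- Events needed for 80% power at 0.5: 7.85 / (0.857 × 0.143 × 0.480) ≈ 134.

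**6. When loss of response can be seen.** Table 5.2-1 has joint counts after Day 85 only at Days 99, 113 and 169. The intervals are 14, 14 and 56 days, so a loss is known only to within one of them.

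**The case against.** The strongest reply is that two links are inferred. Section 7.3.2 does not say who enters the duration analysis, and its sentence on log-rank and Cox does not name the groups. The reference to treatment arms sits with the descriptive summaries, and the rule of active versus placebo first stands in section 7.3.2.1, whose reach back to 7.3.2 can be argued. A reader might infer that the protocol expressly restricts the test to responders and expressly sets it against placebo. It does neither, and the analysis plan, not shown here, might give non-responders zero. This stands as a limit on the wording. It does not remove the point: restriction to responders is what the endpoint's name ordinarily means, log-rank is a between-group test in a placebo-controlled trial, and a zero-duration rule would be a different analysis that the sentence does not describe.

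Second, section 7.3.2.1 already compares ACR response at each study time point and DAS28 response at visits other than Days 29 and 85, without restricting to responders. This also stands, so it would be wrong to infer that the plan has no sound look at persistence. What it lacks is a sound analysis of the duration endpoint itself.

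Third, low power is not a defect: no power is claimed for a secondary endpoint. Fourth, both arms share the visit schedule, so spacing costs resolution and creates ties but does not by itself bias the between-arm comparison. Both replies are right, and neither matter is pressed here.

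**Conclusion.** The point holds as a recommended change to one secondary analysis. If the endpoint is confined to Day 85 responders, as its name suggests, any CAM-3001 versus placebo log-rank or Cox result conditions on a post-randomisation outcome and lacks a randomised interpretation. The expected comparison is about 43 against 7 at the final analysis, or 36 against 6 without Japan. These counts assume that response means the DAS28 definition, that the planning rates hold, and that the planned evaluable numbers are reached. The direction and size of any distortion cannot be known from the protocol.

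A reader might infer that the trial's efficacy conclusion is at risk. It is not: the primary Fisher test does not depend on this analysis, and onset of response can be analysed in all randomised subjects.

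**What to change.** In section 7.3.2, replace the active-placebo log-rank and Cox test of duration with one comparison in all subjects as randomised. Either form would do:

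- response at Day 85 sustained at Days 99, 113 and 169, with Day 85 non-responders counted as failures; or
- days in response after Day 85, with zero for non-responders.

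Name the response definition used and the rule for a missed follow-up visit. Keep the per-visit response comparisons of section 7.3.2.1 alongside. Report duration among responders descriptively, by arm and dose, without a placebo p-value, and note that loss of response is known only to the visit interval. Leave onset of response as planned.

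The cost is a small text change in section 7.3.2 and the matching entry in the analysis plan. It needs no new visits, data or subjects. The downside is small: an all-subject measure mixes achieving a response with keeping it, which is why the descriptive responder summary should stay.
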